#### **6.4.3. Medical History**

Medical history will be coded using the Medical Dictionary for Regulatory Activities (MedDRA) [version 23.1 or a later version if updated during the study] and will be presented by System Organ Class (SOC) and Preferred Term (PT) and total. The SOCs and PTs are to be sorted by Internationally Agreed order SOCs and descending PTs in the total column.

Medical history records will be summarized for the On-Treatment Analysis Set by treatment group and overall as follows:

- The number and percentage of patients with at least one medical history record will be presented.

- The number and percentage of patients with at least one medical history record within each primary SOC and PT will be presented. The summary will be sorted using the internationally agreed order for SOC and using descending order of overall numerical counts for PT. Where terms tie, these will be sorted alphabetically.

Medical history records will be listed by-patient and within-patient by medical history start date for the On-Treatment Analysis Set.

#### 6.4.4. Prior and Concomitant Medications

All medications will be coded using the WHO Drug Global Dictionary (WHO DD), Format B3 [Version Sep 2020 (or a later version if updated during the study)], Anatomical Therapeutic Chemical (ATC) Classification codes.

Prior medications and concomitant medications are defined as follows:

- Prior medications are those taken with a stop date and time prior to the start of the Treatment Period.
- Concomitant medications are those with a start date and time on or after the start of the Treatment Period, or those with a start date and time before the start of the Treatment Period and either a stop date and time on or after the start of the Treatment Period, or are ongoing at the start of the study.

See Section [5.2.3](#) for imputation of missing or partial dates for medication.

Prior and concomitant medications will be summarized separately for the On-Treatment Analysis Set by treatment group and overall as follows:

- The number and percentage of patients with at least one prior / concomitant medication will be presented.
- The number and percentage of patients with at least one prior / concomitant medication within each therapeutic class (ATC Level 2), chemical Subgroup (ATC Level 4), and preferred term will be presented. The summary will be sorted using numerical counts by descending order of Anatomical Group, then descending order of Therapeutic Subgroup, then descending order of preferred term in the total column. Where groups or terms tie these will be sorted alphabetically.

Prior medications and concomitant medications will be listed separately for the On-Treatment Analysis Set. In the listings the relative start and stop day of prior / concomitant medication use will be calculated relative to the first dose date of treatment and will be presented for those patients who received at least one dose of treatment. If the concomitant medication is

“Ongoing” it will be indicated as such in the listing and the relative stop day will not be calculated. Only original dates will be presented in the listing even though the relative day may be based on an imputed date.

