#### 6.6 Permanent study drug discontinuation

Permanent study drug discontinuation (PSDD) is allowed at the Investigator's discretion or patient's request at any time. The Investigator should call the [REDACTED] in case of potential PSDDs.

If a patient has what is expected to be a permanent discontinuation of study drug, the patient should complete PSDD visit procedures outlined in the Assessment Schedule ([Appendix 3](#)). At the PSDD visit, unless the patient has a contraindication to anticoagulation, Investigators should arrange patients to be transitioned to appropriate SoC anticoagulation therapy minimizing any gap in anticoagulation since patients with AF are at underlying risk of stroke and systemic embolism (see [Section 7.1](#)).

Patients who permanently discontinue study drug will have an EoS visit approximately 30 days after the PSDD visit and then will be contacted periodically, approximately every 12 weeks, by telephone for SAEs and endpoints (see [Section 7.2](#)) until the site has been notified by the SSC that the randomized period of the trial has ended at which point the patient's participation in the study can be considered completed. Sites should not enter the patient as "complete" in the eCRF until the study has been declared complete, unless the patient has withdrawn their consent to be followed by all possible methods (i.e., in person, remotely, via third party) and refuses to permit review of the medical records.

In certain situations, patients who have previously permanently discontinued study drug and had an PSDD Visit can be allowed to resume study drug. The Investigator should contact the [REDACTED] to determine whether or not a patient who completed a PSDD visit can resume

study drug.

Any patient who permanently discontinues study drug and also wishes to withdraw consent for participation in the study must complete the protocol-specific withdrawal of consent procedures (see [Section 7.3](#)). The Investigator should contact the [REDACTED] to discuss cases in which a patient wishes to withdraw before the decision is made and withdrawal procedures are begun. Withdrawal procedures can begin only after discussion and confirmation that the patient's desire to withdraw full consent.

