## 6.7 Concomitant treatment

The Investigator must instruct the patient to notify the study staff of any new medications he/she takes after being enrolled into the study.

All prescription medications, OTC drugs including herbal supplements, and significant non-drug therapies (including physical therapy and blood transfusions) administered or taken within the timeframe defined in the entry criteria prior to the start of the study and during the study, must be recorded on the Concomitant medications/Significant non-drug therapies eCRF. Medication entries should be specific to trade and generic name, the single dose and unit, the frequency and route of administration, the start and discontinuation date and the reason for therapy.

Each concomitant drug must be individually assessed against all exclusion criteria/prohibited medication. If in doubt, the Investigator should contact the [REDACTED] during screening or, if the patient is already enrolled, to determine if the patient should continue with study treatment.

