### 6.7.1 Prohibited medication

In case any of the following medications are clinically necessary, no further dosing of the study drug should occur until the investigator has determined that it is safe for the patient to resume study drug:

- Anticoagulants, other than the assigned study drugs, by any route
- Parenteral antiplatelet drugs (except NSAIDs)
- Thrombolytic agents.

For patients in the rivaroxaban arm: use of combined P-gp and strong CYP3A inhibitors such as atazanavir, clarithromycin, dronedarone, indinavir, itraconazole, ketoconazole, nefazodone, nelfinavir, ritonavir, saquinavir, telithromycin, and voriconazole is prohibited as well as other drugs in accordance with local regulations during their time in the study.

For patients in the rivaroxaban arm: use of combined P-gp and strong CYP3A inducers such as rifampin/rifampicin, rifabutin, rifapentine, phenytoin, phenobarbital, primidone, St. John's Wort, and carbamazepine is prohibited, as well as other drugs in accordance with local regulations during their time in the study.

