**Table 7-1 End of Study Transition Guidelines**

Transitioning to	Instructions
Direct oral anticoagulant (DOAC)	Patients should initiate oral DOAC on the same day of the EoT/EoE visit.
Vitamin K antagonist (VKA)	Patients should be given a supply of VKA and instructed to begin therapy 3 to 5 days before the EoT visit. At the EoT visit, measure PT/INR and repeat as frequently as necessary until the PT/INR is therapeutic. Sites may collect repeat INR samples using point of care devices or send for local analysis, in which case results will remain as part of source documentation only.

The EoS visit (in-person or telephone/video-call) will take place approximately 4-weeks after the EoT/EoE visit. This visit will assess patients for a general health and safety check prior to concluding their participation in the study.

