#### 4.1.4. Handling of Intercurrent Events to Reflect the Clinical Question of Interest

Intercurrent events will be handled through a treatment policy strategy.

The following intercurrent events are anticipated during the study:

- Death
- Treatment discontinuation
- Study discontinuation
- Concomitant anticoagulation therapy

**Table 1** describes how intercurrent events will be collected and handled within the analysis.

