### 5.1.3. Treatment Period

Data collected on the day of first dose will be assigned to the Treatment Period if the time (HH:MM) of data collection and time (HH:MM) of first dose of treatment are both recorded, and the data collection time is on or after the time of first dose of treatment. Otherwise, the assessment will be assigned to the screening / baseline period. If the time (HH:MM) of data collection is not recorded but the protocol and / or eCRF includes an instruction to the effect that all Day 1 assessments are to be performed prior to the first dose of treatment or randomization, the data collected at Day 1 will be assigned to the screening / baseline period, otherwise it will be assigned to the Treatment Period.

The Treatment Period is defined as the period from the date of the first dose of treatment up to and including the EoT date as defined in Section 3.1.

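### SAP 6.4.4 sets no end date for concomitant medication, so its by-arm tables mix planned end-of-study anticoagulants with non-study anticoagulants used during randomized treatment; only descriptive tables are affected.

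*SAP*

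**What the plan says.** SAP 6.4.4 (Prior and Concomitant Medications) states: "Concomitant medications are those with a start date and time on or after the start of the Treatment Period". A second limb adds drugs begun earlier that are still being taken at or after that point. Neither limb has an end. The resulting tables are by treatment group for the On-Treatment Analysis Set, and a by-patient listing gives start and stop days relative to first dose.

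The period that 6.4.4 refers to does have an end. SAP 5.1.3 says: "The Treatment Period is defined as the period from the date of the first dose of treatment up to and including the EoT date". Addendum 2.1 then moves the visit-based component of the EoT date to the day before the EoT visit. The addendum lists its changes in sections 2.1 to 2.7, and none touches 6.4.4.

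Protocol Table 7-1 sets out the planned switch at the end of treatment. For a DOAC: "Patients should initiate oral DOAC on the same day of the EoT/EoE visit". For a VKA: "Patients should be given a supply of VKA and instructed to begin therapy 3 to 5 days before the EoT visit". For patients who stop study drug early, protocol 6.6 says that at the PSDD visit, absent a contraindication, "Investigators should arrange patients to be transitioned to appropriate SoC anticoagulation therapy minimizing any gap in anticoagulation". On recording, protocol 6.7 says that medications taken "during the study, must be recorded on the Concomitant medications/Significant non-drug therapies eCRF", with start date, stop date and reason for therapy.

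Protocol 6.7.1 lists "Anticoagulants, other than the assigned study drugs, by any route" among the drugs that require study dosing to be held. SAP 4.1.4 names "Concomitant anticoagulation therapy" as an anticipated intercurrent event.

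**The concern.** In a bleeding trial with an open-label comparator, a reader will want to know how often each arm received another anticoagulant while on randomized treatment. SAP Table 1 makes no adjustment for that event in the primary analysis, so its frequency by arm is part of interpreting the hazard ratio.

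The concomitant-medication table is the natural place to look. As defined, it counts an anticoagulant begun as the planned exit from the trial in the same way as one begun in the middle of treatment, and it has no category to separate the two. The same open end admits antiplatelets or NSAIDs begun after the EoT date. For patients who go on to open-label abelacimab, it also admits drugs begun during the extension, unless the data are cut at the end of the randomized phase.

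**Working it through.** The plan gives no figure to reproduce here. The check applies the rule to dates.

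**Inputs.** The example patient is assumed: last abelacimab injection on day 570 and EoT visit on day 600, consistent with protocol 7.1, which places that visit about 30 days after the last injection.

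- EoT date under SAP 3.1 = min(last dose + 60, EoT visit) = min(630, 600) = day 600.
- EoT date under Addendum 2.1 = min(last dose + 60, EoT visit − 1) = min(630, 599) = day 599.
- DOAC start (Table 7-1): day 600.
- VKA start (Table 7-1): days 600 − 5 = 595 to 600 − 3 = 597.
- A later start, assumed 14 days after the visit: day 614.
- A second assumed patient stops early: last injection day 300, standard-of-care anticoagulant started at day 330, EoT date = min(300 + 60, 600) = day 360.

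**Rule as written:** concomitant if start ≥ day 1. **Rule with an end:** concomitant if also start ≤ EoT date.

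| Anticoagulant start | 6.4.4 as written | Ended at SAP 3.1 EoT date | Ended at Addendum 2.1 EoT date |
|---|---|---|---|
| DOAC, day 600 | counted | counted | not counted |
| VKA, days 595–597 | counted | counted | counted |
| Later start, day 614 | counted | not counted | not counted |
| After early stop, day 330 | counted | counted | counted |

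Three things follow. As written, every start is counted, including one two weeks after the visit. Under the addendum, the visit-day DOAC begins one day after the Treatment Period has ended and is still counted. An end date alone does not remove the VKA, because it begins before the EoT date; it has to be identified by its purpose.

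**Effect on the inferential analyses.** The primary analysis (SAP 6.6.1) censors at the EoT date and does not use 6.4.4, so its change is zero. Sensitivity analysis 3 (SAP 6.6.2) additionally censors when concomitant anticoagulation starts. Its shift is EoT date − min(EoT date, start):

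- DOAC at the visit: 600 − 600 = 0 days under SAP 3.1; 599 − 599 = 0 days under the addendum.
- VKA: 600 − 597 = 3 to 600 − 595 = 5 days under SAP 3.1; 599 − 597 = 2 to 599 − 595 = 4 days under the addendum.
- Early stop: 360 − 330 = 30 days. This is the use that sensitivity analysis 3 is meant to censor, and it is the same whether or not 6.4.4 has an end.

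**The case against.** The strongest reply is that the tables are already limited to on-treatment data. SAP 3.3 says patients are on-treatment through the EoT date and names medications among the summaries that use this set. But 3.3 defines a set of patients and states no cut-off for medication records. SAP 6.7.3 summarizes TEAEs through the end-of-study visit in the same set. One can argue that 6.7.3 is an explicit override of a default EoT limit. That leaves 6.4.4 ambiguous at best, and its literal wording has no limit.

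Second, nothing inferential depends on this, and the information is not lost: the listing shows relative start days, and reason for therapy is collected. Both points stand, and they limit the matter to descriptive tables.

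Third, SAP 2.1 plans a separate analysis plan for the extension. A reader might infer that extension-period drugs will certainly be attributed to the randomized arm. The documents do not support that. They show only that 6.4.4 itself contains no cut.

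Fourth, a reader might infer that this table is the only summary of non-study anticoagulation. That cannot be confirmed, because the exploratory analyses are redacted and the table shells are not among the documents.

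Fifth, not all non-study anticoagulation departs from the protocol. Protocol 6.5.2 permits short-term use after a procedure until study drug resumes, so any breakdown needs a place for temporary interruptions.

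Finally, protocol 7.2 might be cited to show that medications are still collected after treatment ends. It concerns patients who stop early. For completers the support is protocol 6.7.

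**Conclusion.** The point holds as a defect in a definition. The rule in SAP 6.4.4, read with Table 7-1, Addendum 2.1 and protocol 6.7, places planned end-of-study anticoagulants in the concomitant-medication tables by arm, where they cannot be told apart from anticoagulants used during randomized treatment. The primary hazard ratio is unaffected. The planned switch moves sensitivity analysis 3 by 0 days (DOAC) or 2 to 5 days (VKA).

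A reader might go further and infer that the table would be swamped and a real difference between arms hidden. One can build such a figure: share counted = u + (1 − u) × exp(−0.105 × months/12), where u is true on-treatment use, 0.105 = −ln(0.90) is the rate for 10% annual dropout, and every completer switches with no extension. With u of 5% to 15% this gives 0.862 to 0.876 at 18 months and 0.834 to 0.851 at 22 months. If half of completers enter the extension, it gives about 44% to 51%.

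The documents do not support relying on these numbers. Neither u nor a contrast between arms appears anywhere. The 10% in SAP 2.3 is dropout from the study (death, withdrawal, loss to follow-up), not failure to complete treatment. The formula also gives early discontinuers no anticoagulant beyond u, although protocol 6.6 directs them to standard-of-care anticoagulation. The addendum revises dates for patients who enrolled in the extension, so the no-extension case is doubtful. The size of the distortion depends on extension uptake and true on-treatment use, and neither is given.

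**What to change.** In SAP 6.4.4, define concomitant medications for the randomized phase as those taken on or after first dose with a start date on or before the EoT date as amended in Addendum 2.1. The amended date matters: with the SAP 3.1 date, a DOAC started at the visit would still be counted. Tabulate later starts separately as post-treatment medications. This also keeps drugs started in the extension out of the randomized-phase table.

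For anticoagulants, use the recorded start date and reason for therapy to show four rows by arm: started while on study drug; started during a temporary interruption; started after permanent discontinuation; and started as the planned end-of-study transition, including a VKA begun before the EoT visit.

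The cost is a short change to the definition, one extra table, and some classification of anticoagulant records by reason for therapy, which needs review as well as programming. No new data are needed. The addendum records database lock on 08Mar2024, so the change would be documented as a further post-lock change to descriptive output.

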## 6.5. Measurements of Treatment Compliance

Treatment compliance for abelacimab is defined as the number of injections that were actually administered relative to the number of injections that should have been administrated as per the protocol for the duration of actual treatment exposure.

In general, the percentage overall compliance for abelacimab, assessed by injections count, will be calculated as follows:

$$\text{Compliance (\%)} = \frac{\text{Number of injections actually administrated}}{\text{Number of injections that should have been administrated}} \times 100\%$$

Treatment compliance for rivaroxaban is defined as the number of tablets that were actually taken relative to the number of tablets that should have been taken as per the protocol for the duration of actual treatment exposure.

In general, the percentage overall compliance for rivaroxaban, assessed by tablets count, will be calculated as follows:

$$\text{Compliance (\%)} = \frac{(\text{Total Number of tablets dispensed} - \text{Total Number of tablets returned})}{\text{Number of tablets that should have been taken}} \times 100\%$$

The calculated percentage compliance will be categorized as:

- < 80% compliance
- $\geq 80\%$  to  $\leq 125\%$  compliance
- $> 125\%$  compliance

Compliance will be summarized for the On-Treatment Analysis Set by treatment group as follows:

- Percent compliance will be presented by default summary statistics.
- Number and percentage of patients within each of the compliance categories will be presented. Any patients with missing data will be presented as part of a “Missing” category.

Treatment compliance will be listed together with exposure for the On-Treatment Analysis Set. Missing data will not be imputed and only original data for those fields (for example,

date fields) will be presented in the listing together with derived variables such as the calculated compliance (%) and exposure duration.

## 6.6. Primary Analysis

### 6.6.1. Primary Analysis

The primary endpoint variable is defined as time to first event of composite of ISTH-defined major bleeding or CRNM bleeding events occurring from randomization through EoT date. Patients alive and on-study without an event will be censored at the EoT date. Patients lost to follow-up or who otherwise discontinued study follow-up prematurely without experiencing any event will be censored at the EoT date, as defined in Section 3.1. Patients who did not experience any event before death will be censored at the earlier of the date of death and EoT date.

The primary analysis will compare each abelacimab regimen with rivaroxaban for the time from randomization to first occurrence of major or CRNM bleeding in the On-Treatment Analysis Set. For each treatment regimen, the event rates at 6-month intervals will be estimated with 95% confidence intervals (CIs). For each comparison, the time to first event will be tested using the stratified log-rank test and the treatment effect estimated using the Cox proportional hazards model including treatment and the following two stratification factors as covariates:

- Planned use of concomitant antiplatelet medication use (e.g. aspirin and/or P2Y12 inhibitor) for the duration of the trial
- CrCl (Cockcroft-Gault)  $\leq 50$  ml/min

The hazard ratios with 95% CIs and two-sided p-values will be reported for both doses of abelacimab vs. rivaroxaban. A significance level of  $\alpha=0.05$ , without adjustment for multiplicative testing, will be used.

An inverted Kaplan-Meier plot will be drawn and estimates of the event rate at 6-month intervals will be presented.

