### 2.2.3. Exploratory Objectives

### 2.3. Sample Size and Power

The primary endpoint is the composite of major or CNRM bleeding. The study is event driven. At the start of trial it was assumed a HR of 0.60 for each dose of abelacimab compared with rivaroxaban, thereby, a total of at least 166 events would provide at least 80% power for each abelacimab arm vs. rivaroxaban with a 2-sided alpha of 0.05. Given an expected 15% per year event rate in the rivaroxaban arm, a 10% annual dropout rate (death, withdrawal of consent,

lost-to-follow-up), approximately 1,200 patients would provide the requisite number of events over an approximate total trial duration of 27 months.

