#### 4.1.3. Variable Obtained from Each Patient Required to Address the Clinical Question

For each patient in the study, the variable to address the clinical question is time from randomization to first event of composite of ISTH-defined major bleeding or CRNM bleeding events. Patients still alive and on study without an event will be censored at the EoT date. Patients lost to follow-up or who otherwise discontinued follow-up in the study prematurely without experiencing any event will be censored at the EoT date, as defined in Section 3.1. For patients who die without experiencing a primary event before death, the time to event will be censored on the date of death.

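### The 6-month bleeding rates in SAP 6.6.1, read as one minus Kaplan-Meier with deaths censored, modestly overstate each arm's absolute bleeding risk

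*SAP*

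**What the plan says.** SAP 4.1.3 sets the rule for deaths: "For patients who die without experiencing a primary event before death, the time to event will be censored on the date of death". SAP 6.6.1 repeats it for the primary analysis, and 6.6.2 repeats it for the ITT sensitivity analysis.

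For absolute measures, SAP 6.6.1 plans an event rate per arm every six months with 95% confidence intervals, and adds: "An inverted Kaplan-Meier plot will be drawn and estimates of the event rate at 6-month intervals will be presented". It names no estimator. Protocol 10.4 says only that a rate with a confidence interval will be estimated per regimen.

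The estimand text describes death in two ways. SAP 4.1.4 puts all intercurrent events, death among them, under a treatment policy strategy. Table 1 in the same section says that censoring at death reflects a while-alive strategy.

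Other endpoints follow 6.6.1 by reference: both secondary bleeding endpoints (SAP 6.6.3.1 and 6.6.3.2), and the time-to-event exploratory endpoint added in section 2.6 of the SAP addendum. No cumulative incidence or competing-risk analysis appears in the readable text, although the exploratory section 6.6.4 is redacted.

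**The concern.** A patient who dies cannot later have a first bleed. Kaplan-Meier treats a patient censored at death as still able to bleed, at the rate of those who remain. One minus Kaplan-Meier therefore answers what the risk would be if death did not occur. The proportion of patients who actually bleed by a given time is the cumulative incidence, which is lower wherever event-free deaths precede later bleeds.

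Death cannot be ignored in this population: protocol section 1.2.2 gives a mean age of 73.9 years and a mean CHA2DS2-VASc of 4.7, and the sample-size text counts death within its dropout. At stake are the absolute bleeding risks by arm, a main descriptive result of a trial whose purpose is the bleeding profile. The estimate also does not match the while-alive label in Table 1.

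**Working it through.** **Inputs from the documents (SAP 2.3).** "Given an expected 15% per year event rate in the rivaroxaban arm"; "At the start of trial it was assumed a HR of 0.60 for each dose of abelacimab compared with rivaroxaban"; and "a 10% annual dropout rate (death, withdrawal of consent" and loss to follow-up included. With about 1,200 patients allocated 1:1:1, there are about 400 per arm. (In the available copy, the sample-size text in the body of the protocol reads 0.69. The protocol synopsis and the SAP both give 0.60, which is used here.)

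**Reproducing the plan's figure.** The SAP says that "a total of at least 166 events would provide at least 80% power for each" abelacimab arm. By Schoenfeld's formula, events per pair = 4 × (1.960 + 0.842)² / (ln 0.60)² = 31.4 / 0.261 = 120.3. With HR 0.60 in both abelacimab arms, one pair holds about 1.6/2.2 = 72.7% of all events. The total is 120.3 / 0.727 = 165.4, rounded up to 166, and power at 166 events is 80.1%. The planning figures reproduce, so their hazards are a fair basis for the check.

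**Assumption.** The documents give no separate death rate. Let m be the hazard of death before a bleed and before the EoT date. I take 2 to 6% per year, with 10% as a ceiling (the whole planned dropout).

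**Formulas,** with constant hazards and bleeding hazard h = 0.15 per year on rivaroxaban and 0.60 × 0.15 = 0.09 on abelacimab:

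- One minus Kaplan-Meier: 1 − exp(−h t)
- Cumulative incidence: h/(h + m) × [1 − exp(−(h + m) t)]

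**At t = 2 years,** one minus Kaplan-Meier gives 1 − exp(−0.30) = 25.92% on rivaroxaban and 1 − exp(−0.18) = 16.47% on abelacimab, a difference of 9.45 points. Cumulative incidence, with the Kaplan-Meier excess in points in brackets and m equal in all arms:

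| m per year | Rivaroxaban | Each abelacimab arm | Difference |
|---|---|---|---|
| 2% | 25.43% (0.49) | 16.16% (0.32) | 9.27 (0.17) |
| 3% | 25.19% (0.72) | 16.00% (0.47) | 9.19 (0.25) |
| 5% | 24.73% (1.19) | 15.70% (0.77) | 9.03 (0.42) |
| 6% | 24.50% (1.42) | 15.55% (0.92) | 8.95 (0.50) |
| 10% | 23.61% (2.31) | 14.97% (1.50) | 8.63 (0.81) |

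At 12 months the excess is at most 0.66 points, even at the 10% ceiling.

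**Unequal mortality.** With m = 3% on rivaroxaban and 5% on abelacimab, the difference in cumulative incidence is 9.49 points against 9.45 by Kaplan-Meier. With 3% and 6% it is 9.64. The sign changes once the abelacimab death hazard is about 1.55 to 1.6 times that on rivaroxaban.

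**Simulation check** (400,000 per arm, m = 3%, staggered censoring): one minus Kaplan-Meier against Aalen-Johansen was 26.0% against 25.2% on rivaroxaban and 16.5% against 16.0% on abelacimab. Bleeding rates per person-year came out at 0.150 and 0.090, so the cause-specific hazard ratio is not distorted.

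**Precision.** With 400 per arm and complete 24-month follow-up, the standard error is √(0.259 × 0.741/400) = 2.2 points on rivaroxaban and √(0.165 × 0.835/400) = 1.9 points on abelacimab. For their difference it is √(2.2² + 1.9²) = 2.9 points.

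**The case against.** The strongest reply is that little depends on this. The planned treatment effect is the hazard ratio (SAP 4.1.5), tested by a stratified log-rank test. Both compare cause-specific hazards, for which censoring at death is appropriate, so the primary conclusion and the power do not move. That stands in full.

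The size is also small: below one standard error per arm over the assumed range. Only event-free deaths before the EoT date count, and follow-up for this analysis ends no later than 60 days after the last dose. Fatal major bleeds are events, not censored deaths. The 10% dropout includes withdrawal and loss to follow-up, so it is only a ceiling. These points also stand. However, the bias has a known direction, grows with follow-up and does not shrink with more patients.

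The estimator is inferred. If the event rate meant events per person-time, this bias would not arise. But rates at 6-month intervals set beside a Kaplan-Meier plot point to one minus Kaplan-Meier, and if that is not meant, the text still needs to say what is.

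A reader might infer that the absolute benefit of abelacimab is overstated. The documents do not support that as a general claim: it requires similar mortality across arms, no arm-specific death rates are given, and the readable SAP plans no risk difference. The benefit-risk wording in the protocol concerns the DMC and the opening of the extension and does not refer to these rates.

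Finally, Aalen-Johansen with death as the competing event still treats censoring after stopping drug as independent. It corrects for death, not for informative discontinuation.

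**Conclusion.** The point holds for the absolute risks in each arm. As written, the plan leads to 6-month bleeding probabilities that are never below the actual ones and do not fit the while-alive label in Table 1. At 24 months the excess is about 0.5 to 1.4 points on rivaroxaban and 0.3 to 0.9 points on each abelacimab arm. This rests on the plan's own bleeding rates, constant hazards, independent censoring other than death, an assumed mortality of 2 to 6% per year, and the reading of the event rate as one minus Kaplan-Meier.

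A difference that a reader derives from these rates would be 9.45 points instead of 9.27 to 8.95 if mortality is similar across arms; with sufficiently higher mortality on abelacimab the error runs the other way. It would be wrong to read this as a flaw in the primary test. It is a modest reporting bias that is cheap to remove.

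**What to change.** In SAP 6.6.1, name the estimator. Report the 6-month absolute rates, with 95% confidence intervals, as Aalen-Johansen cumulative incidence with death as the competing event, and base any absolute difference on it. Apply this to the secondary bleeding endpoints and to the added exploratory time-to-event endpoint that refer to 6.6.1.

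Keep the Kaplan-Meier plot, because SAP 6.6.2 uses it to assess proportional hazards. Keep the Cox and log-rank analyses as planned. Reconcile the strategy for death between the text of SAP 4.1.4 and Table 1.

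No new data are needed. The cost is some SAP wording, a small amount of programming and slightly lower stated rates. Since the addendum already records changes made after database lock, this one would have to be labelled post-lock as well.
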